3.2 Outcome of AEs

The outcome of the AE should be documented as:

- Recovered / resolved
- Recovering / resolving
- Not recovered / not resolved
- Recovered / resolved with sequelae
- Fatal
- Unknown

3.3 Action taken

The action taken by the Investigator or study staff should be documented as:

- Drug withdrawn
- Dose reduced
- Dose increased
- Dose not changed
- Unknown

-
- Not applicable

3.4 Grading Severity of AE**

Severity refers to the grading of adverse events to assess the severity of symptoms as evaluated by the Investigator or as experienced by the subject. The Investigator will make an assessment of severity (e.g. Grade 1 (mild)-Grade 4 (potentially life threatening)) for each AE and SAE reported during the study in accordance with the following definitions:

Mild/Grade 1: No interference with activity

Moderate/ Grade 2: Some interference with activity not requiring medical intervention

Severe/ Grade 3: Prevents daily activity and requires medical intervention.

Potentially Life Threatening/Grade 4: Emergency room visit or hospitalization

**Any adverse event resulting in Death will be classified as a Grade 5

For further information (see Appendix A, Section 7): *FDA Guidance on Toxicity Grading Scale for Healthy Adult and Adolescent Volunteers Enrolled in Preventive Vaccine Clinical Trials*²⁵

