8.2.2. Injection Site Observations

Each HRIG and vaccine injection site will be examined, and injection site observations will be assessed, pre-dose and 30 min [\pm 5 min] post-dose on Day 0 and at each subsequent clinic visit unless no symptoms are observed.

For injection site reaction (ISR) assessment criteria, refer to the table below:

Local Reaction to Injectable Product	Mild (Grade 1)	Moderate (Grade 2)	Severe (Grade 3)	Potentially Life Threatening (Grade 4)
Pain	Does not interfere with activity	Repeated use of non- narcotic pain reliever > 24 hours or interferes with activity	Any use of narcotic pain reliever or prevents daily activity	Emergency room (ER) visit or hospitalization
Tenderness	Mild discomfort to touch	Discomfort with movement	Significant discomfort at rest	ER visit or hospitalization
Erythema/Redness *	2.5 – 5 cm	5.1 – 10 cm	> 10 cm	Necrosis or exfoliative dermatitis
Induration/Swelling **	2.5 – 5 cm and does not interfere with activity	5.1 – 10 cm or interferes with activity	> 10 cm or prevents daily activity	Necrosis

* In addition to grading the measured local reaction at the greatest single diameter, the measurement should be recorded as a continuous variable.

** Induration/Swelling should be evaluated and graded using the functional scale as well as the actual measurement.

For the complete guidance (see Appendix A, Section 7): Toxicity Grading Scale for Healthy Adult and Adolescent Volunteers Enrolled in Preventive Vaccine Clinical Trials²⁵ :

All injection site reactions (ISR) will be recorded and graded on the ISR eCRF page. However, the investigator will determine if these are AEs. Injection site reactions will be recorded as AEs when the sign/symptoms require concomitant medications, or have an impact on the general condition of the subject as judged by the Investigator. The investigator will use their judgement to record the severity of the AE, using the appended toxicity scale to guide their assessment.

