Hypertension (diastolic) - mm Hg	91 – 95	96 – 100	> 100	ER visit or hospitalization for malignant hypertension
Hypotension (systolic) – mm Hg	85 – 89	80 – 84	< 80	ER visit or hospitalization for hypotensive shock
Respiratory Rate – breaths per minute	17 – 20	21 – 25	> 25	Intubation

* Subject should be at rest for all vital sign measurements.

** Oral temperature; no recent hot or cold beverages or smoking.

*** When resting heart rate is between 60 – 100 beats per minute. Use clinical judgement when characterizing bradycardia among some healthy subject populations, for example, conditioned athletes.

Systemic (General)	Mild (Grade 1)	Moderate(Grade 2)	Severe (Grade 3)	Potentially Life Threatening (Grade 4)
Nausea/vomiting	No interference with activity or 1 – 2 episodes/24 hours	Some interference with activity or > 2 episodes/24 hours	Prevents daily activity, requires outpatient IV hydration	ER visit or hospitalization for hypotensive shock
Diarrhea	2 – 3 loose stools or < 400 gms/24 hours	4 – 5 stools or 400 – 800 gms/24 hours	6 or more watery stools or > 800gms/24 hours or requires outpatient IV hydration	ER visit or hospitalization
Headache	No interference with activity	Repeated use of non-narcotic pain reliever > 24 hours or some interference with activity	Significant; any use of narcotic pain reliever or prevents daily activity	ER visit or hospitalization
Fatigue	No interference with activity	Some interference with activity	Significant; prevents daily activity	ER visit or hospitalization
Myalgia	No interference with activity	Some interference with activity	Significant; prevents daily activity	ER visit or hospitalization

Contains Nonbinding Recommendations

Systemic Illness	Mild (Grade 1)	(Moderate(Grade 2)	Severe (Grade 3)	Potentially Life Threatening (Grade 4)
Illness or clinical adverse event (as defined according to applicable regulations)	No interference with activity	Some interference with activity not requiring medical intervention	Prevents daily activity and requires medical intervention	ER visit or hospitalization

Contains Nonbinding Recommendations

B. Tables for Laboratory Abnormalities

The laboratory values provided in the tables below serve as guidelines and are dependent upon institutional normal parameters. Institutional normal reference ranges should be provided to demonstrate that they are appropriate.

Serum *	Mild (Grade 1)	Moderate (Grade 2)	Severe (Grade 3)	Potentially Life Threatening (Grade 4)**

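### Appendix A 3.4 grades every adverse event by the toxicity scale's generic row, which leaves two combinations without a grade and conflicts with the scale's event-specific rows, with no rule on which prevails

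*Protocol*

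**What the plan says.** Protocol Appendix A 3.4 has the investigator assess severity "for each AE and SAE reported during the study in accordance with the following definitions". The first three grades are:

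- The lowest grade covers events that leave the subject's activity undisturbed; intervention is not mentioned.
- The middle grade reads "Moderate/ Grade 2: Some interference with activity not requiring medical intervention", so an event that needs intervention falls outside it.
- The next grade up reads "Severe/ Grade 3: Prevents daily activity and requires medical intervention", so both conditions must be met.

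Grade 4 is emergency attendance or hospital admission, and a fatal event is Grade 5. The section then cites the toxicity scale in Appendix A Section 7 as further information. Appendix A 5.1 carries the 3.4 grade onto the serious adverse event form.

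Section 7 has a generic Systemic Illness row and separate rows for local reactions, vital signs, named systemic symptoms and laboratory values. For fatigue and myalgia, its Grade 3 is "Significant; prevents daily activity", with no intervention required. Fever and laboratory results are graded by value.

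Protocol 8.2.2 has every injection-site reaction graded on its own eCRF page, using the local-reaction rows. "Injection site reactions will be recorded as AEs when the sign/symptoms require concomitant medications", or when they affect the subject's general condition. The investigator then grades that AE by judgement, "using the appended toxicity scale to guide their assessment".

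Protocol 10.6.1 and SAP 8.h tabulate each subject's maximum severity per term, ordered severe, moderate, mild.

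**The concern.** A severity scale should give each event exactly one grade. In 3.4, Grades 2 and 3 each combine two conditions (degree of interference, and whether there was medical intervention), and the two definitions do not cover all the combinations. A site that follows 3.4 literally will meet events it cannot grade. A site that turns to Section 7 may reach a different grade for the same event, and neither document says which page governs.

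The events concerned are expected in this trial. Protocol 2.8 lists fatigue, fever, headache, myalgia and injection-site pain among the most common reactions to the vaccine, which each subject is scheduled to receive five times. All of them have their own row in Section 7. The study is intended to be multi-center, so sites may well grade differently. At stake is the AE-by-severity summary by arm, which supports Objective 4 (safety and tolerability).

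**Working it through.** There is no stated figure to reproduce. The check is a full listing of cases under 3.4, followed by a comparison with Section 7.

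**Step 1: coverage of 3.4.** Inputs are the Grade 1 to 3 definitions in Appendix A 3.4. Cross interference (none, some, prevents daily activity) with medical intervention (no, yes), excluding emergency attendance and admission: 3 × 2 = 6 combinations. Grade 1 does not mention intervention, so it covers both cells in its row.

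| Interference | No intervention | Intervention |
|---|---|---|
| None | Grade 1 | Grade 1 |
| Some | Grade 2 | no grade |
| Prevents daily activity | no grade | Grade 3 |

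Four of six cells have a grade and two do not.

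**Step 2: source of the gaps.** The Systemic Illness row of Section 7 uses the same conditions. Its Grade 2 is also "Some interference with activity not requiring medical intervention", and its Grade 3 also joins prevented activity to intervention. Section 3.4 is therefore that row, applied to every AE and SAE, including events for which the scale has a dedicated row.

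**Step 3: 3.4 against the dedicated rows.**

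| Event | Appendix A 3.4 | Section 7 row |
|---|---|---|
| Fatigue or myalgia preventing daily activity, no intervention | no grade | 3 |
| Fatigue, some interference, with medical intervention | no grade | 2 |
| Headache treated with a narcotic, no interference | 1 | 3 |
| Fever 39.0–40 °C, no interference | 1 | 3 |
| ALT 5.1–10 × ULN recorded as an AE, no interference | 1 | 3 |
| Hemoglobin fall 2.1–5.0 g/dL recorded as an AE, no interference | 1 | 3 |
| Injection-site pain preventing daily activity, no intervention | no grade | 3 |

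Where both scales give a grade, the gap in these examples is 3 − 1 = 2 grades. The remaining rows pair no grade with Grade 2 or Grade 3.

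**Step 4: one reaction, two records.** The last row can arise within a single subject. The pain is Grade 3 on the injection-site page. If it also becomes an AE because it affects general condition, 3.4 gives it no grade. This holds however medical intervention is read. The other gap does depend on that reading: pain with some interference that needs medication falls outside 3.4 Grade 2 only if medication counts as medical intervention, and the documents do not define the term.

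**Step 5: the tables.** The scale has Grades 1 to 5. The severity order in Protocol 10.6.1 and SAP 8.h names three levels, with no place for Grade 4, Grade 5 or an ungraded event.

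**The case against.** The strongest reply is that 3.4 does not oppose the appended scale. It states the scale's own generic row and refers to Section 7 for the rest, so a sensible investigator would use the specific row where there is one. Much of this stands. A reader might infer that 3.4 contradicts the whole scale, and that is not so: the conflict is with the event-specific rows only, and the two gaps are in the scale's generic row as well. But 3.4 tells the investigator to grade each event by its own definitions and offers Section 7 only as further information. The sensible reading is nowhere stated.

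Injection-site reactions are better protected than other events. All of them are graded by the local-reaction rows on their own page, and 8.2.2 points the AE grade towards the same scale. Severe local reactions are therefore not lost to the trial. What remains is the AE record and the AE table.

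The laboratory examples carry limited weight. Routine hematology and biochemistry are scheduled only at Screening and Day 140, and a result becomes an AE only if the investigator judges it clinically significant. Protocol 10.6.4 also reports changes from baseline and shift tables, so an abnormal value stays visible whatever its AE grade.

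Section 7 places repeated non-narcotic analgesic use in Grade 2 for pain and headache, which suggests that self-medication need not count as medical intervention. This weakens the gap for treated events with some interference. It does not touch the gap for untreated events that prevent activity.

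Finally, safety is compared descriptively without hypothesis tests (Protocol 10.6), and those who assess reactions are blinded (6.6). Misgrading should therefore be similar in the two arms. This stands, and it limits the consequence.

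**Conclusion.** The concern holds in limited form. Read literally, 3.4 gives no grade to two of six combinations. It gives a grade two levels below Section 7 for several fever, headache and laboratory events, and no precedence rule settles the matter. The consequence is confined to the descriptive AE-by-severity tables that support Objective 4. The primary endpoint and its analysis are unaffected.

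Two stronger readings are tempting but not supported. A reader might infer that one event could be ungraded, Grade 1 or Grade 3. It cannot: under 3.4 any one of these events is either ungraded or Grade 1, so the discrepancies come in pairs that belong to different events.

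A reader might also infer a measurable under-count of severe events and a diluted difference between arms. Suppose a share f of would-be Grade 3 subjects were missed equally in both arms, with true proportions p1 and p0. The ratio would be (1 − f)p1 ÷ (1 − f)p0 = p1 ÷ p0, unchanged for any f below 1, and the difference would shrink to (1 − f)(p1 − p0). The documents give neither f nor the expected Grade 3 proportions, and f is above 0 only if sites apply 3.4 literally. The size cannot be estimated from the documents.

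The conclusion assumes that sites grade by the text as written. It does not assume any frequency for the affected events.

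**What to change.** Amend Appendix A 3.4, and carry the same rule into the eCRF completion instructions:

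1. An AE with its own row in Section 7 is graded by that row. Laboratory rows are read against the central laboratory's reference ranges, since the scale itself presents its laboratory limits as guidelines that depend on local ranges. The generic definition is used only for AEs without a row.
2. The generic definition assigns a grade to both uncovered combinations, for example by letting the level of interference alone set Grade 2 or Grade 3, with or without medical intervention.
3. The severity tables in Protocol 10.6.1 and SAP 8.h use this grade and show Grades 4 and 5 in addition to the three levels now listed.

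A different precedence rule would also settle the conflict if it were stated, but the two gaps would still need closing.

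The cost is wording in Appendix A, the eCRF instructions and the table specifications, with no added visits, samples or subjects. The downside is a small departure from the guidance's generic row and possibly a slightly higher Grade 3 count.

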4. ADVERSE EVENT FOLLOW UP

All adverse events will be followed:

- to resolution
- or
- until an underlying condition has been diagnosed
- or
- until the patient's condition has stabilised
- or
- for a period of 28 days following the last administration of the study drug (HRIG or rabies vaccine) or the last study visit, whichever is soonest.

Any new or unresolved AEs noted at the last study visit will be followed up for a further 28 days unless they fulfil the above criteria.

All pregnancies will be followed up until birth and any birth defects will be reported as in the procedures for SAEs (see section 3 and 4).

If the subject becomes pregnant while participating in the study, the pregnancy will not be recorded as an SAE, but will be captured on a Pregnancy Report Form and followed through until delivery or elective/spontaneous termination.

5. REPORTING SERIOUS ADVERSE EVENTS

When an Adverse Event occurs, which fulfils the definition of serious (see Section 2.6 for definition) the Investigator must complete and sign the serious adverse event form and send it within 24 hours to the appropriate contact.,

Medical cover for urgent queries relating to adverse events will be provided on 24 hours / 7 days a week by the following:

[REDACTED]

All SAE reports must be e-mailed or faxed directly to [REDACTED] at [REDACTED] or [REDACTED] (see study reference manual for guidance on providing documentation of SAE).

The Investigator is responsible for expedited reporting of all Serious Adverse Events immediately to BPL and / or the designated CRO except for those that the protocol or Investigator's Brochure identifies as not requiring immediate reporting. This reporting requirement covers any serious adverse events that develop at any point between the date when a subject provides informed consent and up to 28 days after the last administration of the investigational medicinal product (HRIG or rabies vaccine). The investigator is also responsible for reporting to BPL and / or the designated CRO any serious adverse events with an onset date more than 28 days after the last administration of the product if he/she judges the serious adverse event to be possibly, probably or very likely/certainly related to the product.

The immediate report should contain the following as a minimum:

- a suspected investigational medicinal product
- study subject number
- details of the serious adverse event
- classification of SAE
- causality of SAE (if available)

The immediate SAE form should be followed by a detailed, complete SAE form as soon as possible. The immediate report and follow-up reports shall identify subjects by unique code numbers assigned to the latter.

Adverse events and/or laboratory abnormalities identified in the protocol as critical to the evaluation of safety must be reported to BPL and / or the designated CRO by the Investigator according to the reporting requirements within the time periods specified in this protocol.

The investigator must not wait to receive additional information to document fully the event before notification of a SAE, though additional information may be requested. Where applicable, information from relevant laboratory results, hospital case records and autopsy reports should be obtained.

Instances of death, congenital abnormality or an event that is of such clinical concern as to influence the overall assessment of safety, if brought to the attention of the investigator at any time after cessation

of IMP administration and linked by the investigator to this study should be reported to BPL or the designated CRO.

BPL and / or the designated CRO will promptly notify all relevant investigators and the regulatory authorities of findings that could adversely affect the safety of patients, affect the conduct of the study or alter the IEC/IRB approval/favourable opinion of the study. In addition, the sponsor (or designated CRO), will expedite the reporting to all concerned investigators, to the IECs/IRBs, where required, and to the regulatory authorities of all adverse events that are serious, unexpected, and in the opinion of the investigator, related to the IMP.

The investigator will comply with local requirements related to the reporting of SAEs, IND Safety Notification Letters, and other safety information related to the trial to their local IRB.

For reported deaths of a subject, the investigator shall supply BPL and / or the designated CRO (as stated in the Study Reference Manual) and the Independent Ethics Committee (IEC) / Institutional Review Board (IRB) with any additional information requested.

5.1 Completing Serious Adverse Event Forms

Serious Adverse Event (SAE) forms must be completed in a timely manner and contain the following information:

- subject number, randomization number, sex, date of birth, study centre, trial code,
- description of event (where possible a diagnosis should be made rather than just listing symptoms),
- dose, route, date and time of start and last dose,
- date and time of adverse event,
- **all** concomitant medication (copy of concomitant medication page can be appended),
- causal relationship to study medication (as in Section 3.1),
- outcome (as in Section 3.2),
- action taken and treatment given (as in Section 3.3),
- severity (as in Section 3.4),
- classification of serious adverse event (as in Section 2.6),

The SAE form must be signed and dated by the person reporting the SAE. The final report must be signed and dated by the Principal Investigator from the site.

6. BPL'S RESPONSIBILITIES

BPL and / or the designated Contract Research Organisation (CRO) will be responsible for reporting all relevant safety information (including a listing of all SUSARs) to the competent authorities and to the IEC / IRB concerned. In the case of blinded studies, the IEC / IRB and Competent Authority will be provided with an unblinded listing and in order not to bias the study the listing will be provided by

an independent person. Safety reports will be issued in accordance with local relevant procedures (as a minimum on an annual basis).

BPL and / or the designated CRO will inform the relevant Competent Authority(ies) in line with regulatory guidelines on adverse events occurring during the trial. The investigator retains the right to inform the relevant Competent Authority(ies) if he/she so desires but must inform BPL and / or the designated CRO (as stated in the Study Reference Manual) so that duplicate reports to the competent authority(ies) can be highlighted.

BPL and / or the designated CRO will inform all investigators of all suspected unexpected serious adverse reactions occurring during the study or findings that could adversely affect the safety of subjects.

7. TOXICITY GRADING SCALE FOR HEALTHY ADULT AND ADOLESCENT VOLUNTEERS ENROLLED IN PREVENTIVE VACCINE CLINICAL TRIALS

Guidance for Industry

Toxicity Grading Scale for Healthy Adult and Adolescent Volunteers Enrolled in Preventive Vaccine Clinical Trials

Additional copies of this guidance are available from the Office of Communication, Training and Manufacturers Assistance (HFM-40), [name], or by calling [name] or [contact], or from the Internet at <http://www.fda.gov/cber/guidelines.htm>.

For questions on the content of this guidance, contact the Division of Vaccines and Related Products Applications, Office of Vaccines Research and Review at [contact].

U.S. Department of Health and Human Services
Food and Drug Administration
Center for Biologics Evaluation and Research
September 2007

Contains Nonbinding Recommendations**Table of Contents**

I.	INTRODUCTION.....	1
II.	BACKGROUND.....	2
III.	TOXICITY GRADING SCALE TABLES.....	2
	A. Tables for Clinical Abnormalities.....	3
	B. Tables for Laboratory Abnormalities.....	6
IV.	REFERENCES.....	8

Contains Nonbinding Recommendations

Guidance for Industry
Toxicity Grading Scale for Healthy Adult and Adolescent
Volunteers Enrolled in Preventive Vaccine Clinical Trials

This guidance represents the Food and Drug Administration's (FDA's) current thinking on this topic. It does not create or confer any rights for or on any person and does not operate to bind FDA or the public. You can use an alternative approach if the approach satisfies the requirements of the applicable statutes and regulations. If you want to discuss an alternative approach, contact the appropriate FDA staff. If you cannot identify the appropriate FDA staff, call the appropriate number listed on the title page of this guidance.

I. INTRODUCTION

Preventive vaccines are usually developed to prevent disease in a healthy population. The Office of Vaccines Research and Review, Center for Biologics Evaluation and Research, regulates preventive vaccines under authority of section 351 of the Public Health Service Act (42 U.S.C. 262), as well as specific sections of the Federal Food, Drug, and Cosmetic Act, and reviews investigational new drug applications (INDs) and biologics license applications (BLAs). (See, for example, Title 21 Code of Federal Regulations (CFR) Parts 312, 600, and 601). Most of the clinical trials of preventive vaccines conducted to support INDs and BLAs enroll healthy volunteers in all phases of vaccine testing. The enrollment of healthy volunteers warrants a very low tolerance for risk in those clinical trials.

This guidance provides you, sponsors, monitors, and investigators of vaccine trials, with recommendations on assessing the severity of clinical and laboratory abnormalities in healthy adult and adolescent volunteers enrolled in clinical trials. The grading system described in the table can also be useful in defining a particular study's stopping rules (e.g., a certain number of adverse events, as defined in the table, may call for stopping the study). Less extreme observations (e.g., mild) may not require discontinuing the study vaccine but can still contribute to evaluating safety by identifying parameters to focus upon in subsequent product development. Uniform criteria for categorizing toxicities in healthy volunteers can improve comparisons of safety data among groups within the same study and also between different studies. We, FDA, recommend using toxicity grading scale tables, provided below, as a guideline for selecting the assessment criteria to be used in a clinical trial of a preventive vaccine. We recommend incorporation of such appropriate, uniform, criteria into the investigational plan, case report forms, and study reports and correspondence with FDA, sponsors, monitors, investigators, and IRBs.

This guidance finalizes the draft guidance of the same title dated April 2005 (70 FR 22664, May 2, 2005).

Contains Nonbinding Recommendations

FDA's guidance documents, including this guidance, do not establish legally enforceable responsibilities. Instead, guidances describe FDA's current thinking on a topic and should be viewed only as recommendations, unless specific regulatory or statutory requirements are cited. The use of the word *should* in FDA's guidances means that something is suggested or recommended, but not required.

II. BACKGROUND

Standardized toxicity assessment scales have been widely used to evaluate products treating specific diseases. For example, the National Cancer Institute's Common Toxicity Criteria Scale and the Division of AIDS' Toxicity Grading Scale standardize the evaluation of adverse events among patients with cancer and HIV/AIDS, respectively (Refs. 1, 2). The defined toxicity parameters in those scales are designed for patients who may already experience mild, moderate, or severe adverse clinical or laboratory events due to the disease process, and may not be appropriate for healthy volunteers.

In the development of the toxicity grading scales for healthy volunteers, we chose parameter limit values based on published information, when such values were available (Refs. 1-6). For example, the Brighton Collaboration has developed case definitions and guidelines to evaluate some adverse events associated with administering vaccines (Ref. 3). In some cases, parameter limit values were based on clinical experience and experience reviewing vaccine clinical trials that enroll normal healthy subjects.

Toxicity grading scales for laboratory abnormalities should consider the local laboratory reference values when the parameter limit values are defined. The characterization of laboratory parameters among some populations of healthy adults and adolescents may require the exercise of clinical judgment, for example, consideration of the potential for ethnic differences in white blood cell (WBC) counts or gender differences in creatine phosphokinase (CPK) values.

III. TOXICITY GRADING SCALE TABLES

Adverse events in a clinical trial of an investigational vaccine must be recorded and monitored and, when appropriate, reported to FDA and others involved in an investigation (sponsors, IRBs, and investigators). (See, for example, 21 CFR 312.32, 312.33, 312.50, 312.55, 312.56, 312.60, 312.62, 312.64, 312.66). Although the use of a toxicity grading scale for adverse events would not replace these regulatory requirements, using a scale to categorize adverse events observed during a clinical trial may assist you in monitoring safety and making required reports. Nonetheless, we believe that categorization or grading of data as outlined in this document is supplementary to and should not replace full and complete data analysis.

These guidelines for toxicity grading scales are primarily intended for healthy adult and adolescent volunteers. The parameters in the tables below are not necessarily applicable to every clinical trial of healthy volunteers. The parameters monitored should be appropriate for the specific study vaccine. For some preventive vaccines under development, it may be appropriate

Contains Nonbinding Recommendations

to include additional parameters to be monitored during a clinical trial or to alter the choice of values in the toxicity table. For example, additional parameters might be added based on one or more of the following: safety signals observed in pre-clinical toxicology studies, the biological plausibility of the occurrence of certain adverse events, or previous experience with a similar licensed product.

As discussed above, the tables do not represent a recommendation to monitor all the listed parameters in all clinical trials of healthy volunteers, nor do the tables represent all possible parameters to be monitored. In addition, these tables do not represent study inclusion or exclusion criteria. We recommend that the parameters monitored be appropriate for the study vaccine administered to healthy volunteers participating in the clinical trial.

A. Tables for Clinical Abnormalities

Local Reaction to Injectable Product	Mild (Grade 1)	Moderate(Grade 2)	Severe (Grade 3)	Potentially Life Threatening (Grade 4)
Pain	Does not interfere with activity	Repeated use of non-narcotic pain reliever > 24 hours or interferes with activity	Any use of narcotic pain reliever or prevents daily activity	Emergency room (ER) visit or hospitalization
Tenderness	Mild discomfort to touch	Discomfort with movement	Significant discomfort at rest	ER visit or hospitalization
Erythema/Redness *	2.5 – 5 cm	5.1 – 10 cm	> 10 cm	Necrosis or exfoliative dermatitis
Induration/Swelling **	2.5 – 5 cm and does not interfere with activity	5.1 – 10 cm or interferes with activity	> 10 cm or prevents daily activity	Necrosis

* In addition to grading the measured local reaction at the greatest single diameter, the measurement should be recorded as a continuous variable.

** Induration/Swelling should be evaluated and graded using the functional scale as well as the actual measurement.

Contains Nonbinding Recommendations

Vital Signs *	Mild (Grade 1)	Moderate(Grade 2)	Severe (Grade 3)	Potentially Life Threatening (Grade 4)
Fever (°C) ** (°F) **	38.0 – 38.4 100.4 – 101.1	38.5 – 38.9 101.2 – 102.0	39.0 – 40 102.1 – 104	> 40 > 104
Tachycardia - beats per minute	101 – 115	116 – 130	> 130	ER visit or hospitalization for arrhythmia
Bradycardia - beats per minute***	50 – 54	45 – 49	< 45	ER visit or hospitalization for arrhythmia
Hypertension (systolic) - mm Hg	141 – 150	151 – 155	> 155	ER visit or hospitalization for malignant hypertension
Hypertension (diastolic) - mm Hg	91 – 95	96 – 100	> 100	ER visit or hospitalization for malignant hypertension
Hypotension (systolic) – mm Hg	85 – 89	80 – 84	< 80	ER visit or hospitalization for hypotensive shock
Respiratory Rate – breaths per minute	17 – 20	21 – 25	> 25	Intubation

* Subject should be at rest for all vital sign measurements.

** Oral temperature; no recent hot or cold beverages or smoking.

*** When resting heart rate is between 60 – 100 beats per minute. Use clinical judgement when characterizing bradycardia among some healthy subject populations, for example, conditioned athletes.

Systemic (General)	Mild (Grade 1)	Moderate(Grade 2)	Severe (Grade 3)	Potentially Life Threatening (Grade 4)
Nausea/vomiting	No interference with activity or 1 – 2 episodes/24 hours	Some interference with activity or > 2 episodes/24 hours	Prevents daily activity, requires outpatient IV hydration	ER visit or hospitalization for hypotensive shock
Diarrhea	2 – 3 loose stools or < 400 gms/24 hours	4 – 5 stools or 400 – 800 gms/24 hours	6 or more watery stools or > 800gms/24 hours or requires outpatient IV hydration	ER visit or hospitalization
Headache	No interference with activity	Repeated use of non-narcotic pain reliever > 24 hours or some interference with activity	Significant; any use of narcotic pain reliever or prevents daily activity	ER visit or hospitalization
Fatigue	No interference with activity	Some interference with activity	Significant; prevents daily activity	ER visit or hospitalization
Myalgia	No interference with activity	Some interference with activity	Significant; prevents daily activity	ER visit or hospitalization

Contains Nonbinding Recommendations

Systemic Illness	Mild (Grade 1)	(Moderate(Grade 2)	Severe (Grade 3)	Potentially Life Threatening (Grade 4)
Illness or clinical adverse event (as defined according to applicable regulations)	No interference with activity	Some interference with activity not requiring medical intervention	Prevents daily activity and requires medical intervention	ER visit or hospitalization

Contains Nonbinding Recommendations

B. Tables for Laboratory Abnormalities

The laboratory values provided in the tables below serve as guidelines and are dependent upon institutional normal parameters. Institutional normal reference ranges should be provided to demonstrate that they are appropriate.

Serum *	Mild (Grade 1)	Moderate (Grade 2)	Severe (Grade 3)	Potentially Life Threatening (Grade 4)**
Sodium – Hyponatremia mEq/L	132 – 134	130 – 131	125 – 129	< 125
Sodium – Hypernatremia mEq/L	144 – 145	146 – 147	148 – 150	> 150
Potassium – Hyperkalemia mEq/L	5.1 – 5.2	5.3 – 5.4	5.5 – 5.6	> 5.6
Potassium – Hypokalemia mEq/L	3.5 – 3.6	3.3 – 3.4	3.1 – 3.2	< 3.1
Glucose – Hypoglycemia mg/dL	65 – 69	55 – 64	45 – 54	< 45
Glucose – Hyperglycemia				Insulin requirements or hyperosmolar coma
Fasting – mg/dL	100 – 110	111 – 125	>125	
Random – mg/dL	110 – 125	126 – 200	>200	
Blood Urea Nitrogen BUN mg/dL	23 – 26	27 – 31	> 31	Requires dialysis
Creatinine – mg/dL	1.5 – 1.7	1.8 – 2.0	2.1 – 2.5	> 2.5 or requires dialysis
Calcium – hypocalcemia mg/dL	8.0 – 8.4	7.5 – 7.9	7.0 – 7.4	< 7.0
Calcium – hypercalcemia mg/dL	10.5 – 11.0	11.1 – 11.5	11.6 – 12.0	> 12.0
Magnesium – hypomagnesemia mg/dL	1.3 – 1.5	1.1 – 1.2	0.9 – 1.0	< 0.9
Phosphorous – hypophosphatemia mg/dL	2.3 – 2.5	2.0 – 2.2	1.6 – 1.9	< 1.6
CPK – mg/dL	1.25 – 1.5 x ULN***	1.6 – 3.0 x ULN	3.1 – 10 x ULN	> 10 x ULN
Albumin – Hypoalbuminemia g/dL	2.8 – 3.1	2.5 – 2.7	< 2.5	--
Total Protein – Hypoproteinemia g/dL	5.5 – 6.0	5.0 – 5.4	< 5.0	--
Alkaline phosphate – increase by factor	1.1 – 2.0 x ULN	2.1 – 3.0 x ULN	3.1 – 10 x ULN	> 10 x ULN
Liver Function Tests –ALT, AST increase by factor	1.1 – 2.5 x ULN	2.6 – 5.0 x ULN	5.1 – 10 x ULN	> 10 x ULN
Bilirubin – when accompanied by any increase in Liver Function Test increase by factor	1.1 – 1.25 x ULN	1.26 – 1.5 x ULN	1.51 – 1.75 x ULN	> 1.75 x ULN
Bilirubin – when Liver Function Test is normal: increase by factor	1.1 – 1.5 x ULN	1.6 – 2.0 x ULN	2.0 – 3.0 x ULN	> 3.0 x ULN
Cholesterol	201 – 210	211 – 225	> 226	---
Pancreatic enzymes – amylase, lipase	1.1 – 1.5 x ULN	1.6 – 2.0 x ULN	2.1 – 5.0 x ULN	> 5.0 x ULN

* The laboratory values provided in the tables serve as guidelines and are dependent upon institutional normal parameters. Institutional normal reference ranges should be provided to demonstrate that they are appropriate.

** The clinical signs or symptoms associated with laboratory abnormalities might result in characterization of the laboratory abnormalities as Potentially Life Threatening (Grade 4). For example, a low sodium value that falls within a grade 3 parameter (125-129 mEq/L) should be recorded as a grade 4 hyponatremia event if the subject had a new seizure associated with the low sodium value.

***ULN[†] is the upper limit of the normal range.

Contains Nonbinding Recommendations

Hematology *	Mild (Grade 1)	Moderate (Grade 2)	Severe (Grade 3)	Potentially Life Threatening (Grade 4)
Hemoglobin (Female) - gm/dL	11.0 – 12.0	9.5 – 10.9	8.0 – 9.4	< 8.0
Hemoglobin (Female) change from baseline value - gm/dL	Any decrease – 1.5	1.6 – 2.0	2.1 – 5.0	> 5.0
Hemoglobin (Male) - gm/dL	12.5 – 13.5	10.5 – 12.4	8.5 – 10.4	< 8.5
Hemoglobin (Male) change from baseline value – gm/dL	Any decrease – 1.5	1.6 – 2.0	2.1 – 5.0	> 5.0
WBC Increase - cell/mm ³	10,800 – 15,000	15,001 – 20,000	20,001 – 25,000	> 25,000
WBC Decrease - cell/mm ³	2,500 – 3,500	1,500 – 2,499	1,000 – 1,499	< 1,000
Lymphocytes Decrease - cell/mm ³	750 – 1,000	500 – 749	250 – 499	< 250
Neutrophils Decrease - cell/mm ³	1,500 – 2,000	1,000 – 1,499	500 – 999	< 500
Eosinophils - cell/mm ³	650 – 1500	1501 - 5000	> 5000	Hypereosinophilic
Platelets Decreased - cell/mm ³	125,000 – 140,000	100,000 – 124,000	25,000 – 99,000	< 25,000
PT – increase by factor (prothrombin time)	1.0 – 1.10 x ULN**	1.11 – 1.20 x ULN	1.21 – 1.25 x ULN	> 1.25 ULN
PTT – increase by factor (partial thromboplastin time)	1.0 – 1.2 x ULN	1.21 – 1.4 x ULN	1.41 – 1.5 x ULN	> 1.5 x ULN
Fibrinogen increase - mg/dL	400 – 500	501 – 600	> 600	--
Fibrinogen decrease - mg/dL	150 – 200	125 – 149	100 – 124	< 100 or associated with gross bleeding or disseminated intravascular coagulation (DIC)

* The laboratory values provided in the tables serve as guidelines and are dependent upon institutional normal parameters. Institutional normal reference ranges should be provided to demonstrate that they are appropriate.

** "ULN" is the upper limit of the normal range.

Urine *	Mild (Grade 1)	Moderate (Grade 2)	Severe (Grade 3)	Potentially Life Threatening (Grade 4)
Protein	Trace	1+	2+	Hospitalization or dialysis
Glucose	Trace	1+	2+	Hospitalization for hyperglycemia
Blood (microscopic) – red blood cells per high power field (rbc/hpf)	1 - 10	11 – 50	> 50 and/or gross blood	Hospitalization or packed red blood cells (PRBC) transfusion

* The laboratory values provided in the tables serve as guidelines and are dependent upon institutional normal parameters. Institutional normal reference ranges should be provided to demonstrate that they are appropriate.

Contains Nonbinding Recommendations

IV. REFERENCES

1. National Cancer Institute Common Toxicity Criteria, April 30, 1999. (<http://ctep.cancer.gov/reporting/CTC-3.html>)
